- c: Subjects may initiate the practice of self-administration with direct supervision by the Investigator or qualified delegate.
- d: Self-administration supervised by the Investigator or qualified delegate at the study site may continue after Dosing Visit 8 until the subject (or caregiver) feels confident with the technical and medical aspects and is deemed independent for self-administration. Details regarding self-administration will be documented and entered in CRF.
- e: When deemed independent (ie, subjects [or caregivers] are able to correctly reconstitute study drug, access a vein for infusion, and successfully administer the drug on at least 2 consecutive training visits), a subject may elect to self-administer doses of investigational product at home or at the study site. The Investigator's acknowledgement that a subject is certified for independent self-administration will be entered in the CRF.
- f: Subjects (or caregivers) will be allowed to self-administer at the study site. The Investigator or qualified delegate will be available for follow-up training if any of the necessary skills on self-administration have not been retained and to address any issues from the subject's perspective.
- g: Study personnel will contact the subject (or caregivers) by telephone to check on study compliance/competency with self-administration, document any AEs, and update any concomitant medications. Telephone contact will be documented in the source notes at the study site.

See Schedule 3 for clinical study assessments at the Early Discontinuation Visit (if applicable) and the 1-Week and 1-Month Post-treatment Follow-up Visits.

Page 26 30 Aug 2016

Protocol 0624-209 with Amendments 1, 2, 3, 4, and 5 CINRYZE (C1 inhibitor [human])

Schedule 3: Clinical Study Assessments – Early Discontinuation Visit and 1-week and 1-month Post-treatment Follow-up Visits

| Procedure | Early Discontinuation Visit ^a [If Applicable] | 1-Week (±1 day) Post-treatment Visit [All Subjects] | 1-Month (30 ±2 days) Post-treatment Visit [All Subjects] |
|--|---|---|--|
| Physical exam update | X | | |
| Concomitant/post-treatment medications | X | X | X |
| Body weight | X | | |
| Vital signs (BP, pulse) b | X | | |
| Hematology and clinical chemistry | X | | |
| Urinalysis with microscopy | X | | |
| Coagulation (PT, aPTT, INR) | X | | |
| Pregnancy testing ^c | X | | |
| Daily angioedema attack monitoring and study diary | X ^d | X | |
| Adverse events/SAEs ^e | X | X | X |
| Immunogenicity (C1 INH antibody) | X | | X |
| Quality of life questionnaire (AE-QoL) | X | | |
| PK/PD assessments | X ^f | | |

AE-QoL=angioedema quality of life; aPTT=activated partial thromboplastin time; BP=blood pressure; C1 INH=C1 inhibitor; INR=international normalized ratio; PD=pharmacodynamics; PK=pharmacokinetics; PT=prothrombin time; SAE=serious adverse event

- a: If a subject prematurely discontinues investigational product, regardless of the reason, the Early Discontinuation Visit procedures listed in Schedule 3 are to be performed as completely as possible. Whenever possible, all discontinued subjects should also complete the 1-Week and 1-Month Post-treatment Follow-up visits.
- b: Vital signs will be measured using standard methods at each study site.
- c: All females of childbearing potential (in accordance with standards at the site).
- d: Subjects who prematurely discontinue should complete the study diary on the day of discontinuation.
- e: Adverse events will be collected through 7 days after the last dose of investigational product. Investigators will report all serious adverse events (SAEs) that occur up to 30 days after the last dose of study drug to PAREXEL International Pharmacovigilance. In addition, SAEs considered by the Investigator to be related to study drug that occur >30 days after the last dose will be reported.
- f: If a subject prematurely discontinues on a blood sample collection day for PK/PD assessments (see Schedule 4), every effort should be made to collect the PK/PD sample(s) according to schedule. If a subject discontinues on a day when PK/PD assessments are not scheduled, a single PK/PD blood sample should be collected with sampling time recorded in the CRF.

Schedule 4: Blood Sample Collection Time Points for PK/PD Assessments

| C1 INH Antigen (Protein Volume), Functional C1 INH Activity (Potency), | T | REATMENT PERIO | D (BY STUDY WEE | K) | Early |
|---|----------------|----------------|-----------------|-----------------|--------------------------|
| and Complement C4 | Week 1 | Week 2 | Week 3 | Week 12 | Discontinuation Visit |
| Sample Time | Dosing Visit 1 | Dosing Visit 3 | Dosing Visit 5 | Dosing Visit 24 | [If Applicable] |
| Prior to infusion of study drug | X ^a | X | X | X | |
| 0.5 hour after start of infusion | X ^b | | | X ^b | |
| 1 hour after start of infusion | X ^c | | | X ^c | |
| 2 hours after start of infusion | X ^c | | | X ^c | X g |
| 6 hours after start of infusion | X ^c | | | X ^c | A |
| 24 hours after start of infusion | X ^d | | | X ^d | |
| 48 hours after start of infusion | X ^d | | | X ^d | |
| 72 hours after start of infusion | X d, e | | | X ^d | |
| 96 hours after start of infusion | X d, f | | | X ^d | |

C1 INH=C1 inhibitor; PD=pharmacodynamics; PK=pharmacokinetics

- a: C1q concentration will also be assessed from the baseline sample (pre-infusion at Dosing Visit 1).
- b: Collect within ± 5 min of the specified time.
- c: Collect within \pm 15 min of the specified time.
- d: Collect within ± 2 h of the specified time.
- e: If Dose 2 is scheduled to be administered 3 days after Dose 1, the 72-hour sample should be collected pre-infusion and the 96-hour sample should be omitted.
- f: If Dose 2 is scheduled to be administered 4 days after Dose 1, the 96-hour sample should be collected pre-infusion.
- g: If a subject prematurely discontinues on a day when PK/PD assessments are scheduled every effort should be made to collect the PK/PD sample(s) as indicated. If a subject discontinues on a day when PK/PD assessments are not scheduled, a single PK/PD blood sample should be collected with sampling time recorded in the CRF.

NOTE: If a subject presents to the site with a breakthrough angioedema attack, every effort should be made to obtain a PK blood sample before treatment. In addition, if the subject receives CINRYZE for treatment of the attack, every effort should be made to obtain a 1-hour post-treatment sample; if a second dose of CINRYZE is administered, an additional 1-hour post-treatment sample should be obtained if possible. These samples will be collected as an unscheduled visit and analyzed for C1 INH antigen (protein volume) and functional C1 INH activity (potency).

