It is recommended that treatment of breakthrough attacks (ie, angioedema attacks that occur during long-term prevention therapy with CINRYZE) occurs at the investigational site whenever possible so that clinical assessments can be completed as specified. It is preferred that subjects receive CINRYZE within 4 hours but not more than 8 hours after the onset of breakthrough attack symptoms if treatment can occur at the investigational site.

Adverse events will be recorded from the time the informed consent is signed through 7 days after the last dose of investigational product. This includes events occurring during the screening phase of the study, regardless of whether or not the investigational product is administered. In addition, the investigator will report all SAEs that occur through 30 days after the last dose of investigational product to PAREXEL International Pharmacovigilance and the respective Independent Reviewing Authority according to local reporting requirements.

Post-treatment follow-up visits will be performed 1 week (± 1 day) and 1 month (30 ± 2 days) after the last dose of study drug. If a subject prematurely discontinues investigational product, regardless of the reason, the Early Discontinuation Visit procedures listed in Schedule 3 are to be performed as completely as possible. Whenever possible, all discontinued subjects should also complete the 1-Week and 1-Month Post-treatment Follow-up visits.

The schedules of study procedures are provided immediately following the synopsis:

- Schedule 1: Clinical Study Assessments Screening and Treatment Period;
- Schedule 2: Investigational Product and Self-administration Training:
- Schedule 3: Clinical Study Assessments Early Discontinuation Visit and 1-Week and 1-Month Post-treatment Follow-up Visits;
- Schedule 4: Blood Sample Collection Time Points for PK/PD Assessments.

Study Diary

Throughout the study, subjects (or caregivers) will use a study diary each day to document specific information about any angioedema attack symptoms that occur (eg, including the location, severity, pain score, and duration of symptoms) and details on self-administration of investigational product. At the first dosing visit (Dosing Visit 1), study personnel will instruct each subject (or caregiver) how to complete the study diary.

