5.5.2 Thrombotic or Thromboembolic Event

If a thrombotic or thromboembolic (T/TE) event occurs in any subject, no further enrollment will occur pending a complete review of all available data. Other enrolled subjects will continue with study drug administration and procedures. Following a safety review of the T/TE event, study enrollment may be restarted if it is determined that the event is not related to study drug or other C1 inhibitors, which may have been administered for an angioedema attack.

If a T/TE event occurs in any subject, study drug administration for that subject will be interrupted; however, other study procedures will continue, as deemed appropriate by the Investigator in conjunction with the Sponsor. Investigators will comply with protocol-defined algorithms to assist in the diagnosis and management of all suspected T/TE events (see Appendix 2). Following a complete medical review by the Sponsor in conjunction with the Investigator, dosing with study drug may be resumed to complete a total of 24 doses if it is determined that the T/TE event is not related to study drug. Study procedures, including PK/PD testing, will resume relative to dosing. If study drug cannot be restarted within 30 days of temporary interruption, the subject will be discontinued from treatment and will follow the schedule of assessments for the Early Discontinuation Visit and the 1-Week and 1-Month Post-treatment Follow-up Visits (see Schedule 3).

Protocol 0624-209 with Amendments 1, 2, 3, 4, and 5 CINRYZE (C1 inhibitor [human])

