9 ADVERSE AND SERIOUS ADVERSE EVENTS ASSESSMENT

9.1 Definition of Adverse Events, Period of Observation, Recording of Adverse Events

An **AE** is any untoward medical occurrence in a clinical investigation subject administered a pharmaceutical product and that does not necessarily have a causal relationship with this treatment. An AE can therefore be any unfavorable and unintended sign (including an abnormal laboratory finding), symptom, or disease temporally associated with the use of a medicinal (investigational) product, whether or not related to the medicinal (investigational) product (ICH Guidance E2A 1995).

All AEs are collected from the time the informed consent is signed until the defined follow-up period stated in Section 3. This includes events occurring during the screening phase of the study, regardless of whether or not investigational product is administered. Where possible, a diagnosis rather than a list of symptoms should be recorded. If a diagnosis has not been made, then each symptom should be listed individually. All AEs should be captured on the appropriate AE pages in the CRF and in source documents. In addition to untoward AEs, unexpected benefits outside the investigational product indication should also be captured on the AE CRF.

All AEs must be followed to closure (the subject's health has returned to his/her baseline status or all variables have returned to normal), regardless of whether the subject is still participating in the study. Closure indicates that an outcome is reached, stabilization achieved (the Investigator does not expect any further improvement or worsening of the event), or the event is otherwise explained. When appropriate, medical tests and examinations are performed so that resolution of event(s) can be documented.

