9.2.4 Serious Adverse Event Collection Time Frame

All SAEs (regardless of relationship to study) are collected from the time the subject signs the informed consent up to 30 days after the last dose of study drug, and must be reported to PAREXEL International Pharmacovigilance within 24 hours of the first awareness of the event.

In addition, any SAE(s) considered "related" to the investigational product and discovered by the Investigator at any interval after the study has completed must be reported to PAREXEL International Pharmacovigilance within 24 hours of the first awareness of the event.

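### Any thrombotic event halts enrollment, but after day 7 post-dose the protocol requires only serious adverse events to be recorded, so a non-serious thrombotic event on days 8 to 30 carries no stated recording duty

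*Protocol*

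**What the plan says.** **AE recording.** The Synopsis (Study Design) and Section 3 of the protocol state: "Adverse events will be recorded from the time the informed consent is signed through 7 days after the last dose of investigational product". Section 6.2 repeats the limit, and Schedule 3, footnote e, applies it to the post-treatment visits: "Adverse events will be collected through 7 days after the last dose of investigational product". Section 9.1 sets no limit of its own; it collects AEs "until the defined follow-up period stated in Section 3".

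**SAE recording.** Section 9.2.4 collects all SAEs, whatever their cause, "up to 30 days after the last dose of study drug, and must be reported to PAREXEL International Pharmacovigilance". Related SAEs have no end date: those "discovered by the Investigator at any interval after the study has completed must be reported".

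**The study-level halt.** Section 5.5.2 states: "If a thrombotic or thromboembolic (T/TE) event occurs in any subject, no further enrollment will occur pending a complete review of all available data". Neither seriousness nor time since the last dose is a condition.

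**Visits.** The Synopsis and Section 3 state: "Post-treatment follow-up visits will be performed 1 week (± 1 day) and 1 month (30 ± 2 days) after the last dose of study drug". Schedule 3 marks the AE/SAE row at both visits. Section 6.2 has subjects asked about AEs at every study visit, and Section 6.5.2 records concomitant medication, with its indication, through the 1-Month visit.

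**The concern.** The rule that acts on T/TE events is wider than the rule that collects them. Section 5.5.2 covers any T/TE event. From day 8, the collection rule covers only events judged serious. A site could hear of a non-serious thrombosis at the 1-Month visit, follow Schedule 3, footnote e, to the letter, and make no AE entry.

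Safety and tolerability come first in the list of objectives, and T/TE is the only event that stops enrollment under Section 5.5; an anaphylactic reaction ends dosing only for the subject concerned. The overseas open-label prevention study described in Section 1.1.2 had 5 serious thrombotic events. With a minimum of 6 completers planned, one unrecorded T/TE event would be a noticeable part of the thrombosis evidence.

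**Working it through.** The plan gives no figure to reproduce. The check compares the passages and counts days, with day 0 as the last dose.

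**1. What must be recorded, by period**

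| Days after last dose | Non-serious T/TE event | Serious T/TE event | Within the reach of Section 5.5.2? |
|---|---|---|---|
| Up to 7 | Recorded as an AE | Recorded and reported as an SAE | Yes |
| 8 to 30 | No stated duty to record | Recorded and reported as an SAE | Yes |
| After 30 | No stated duty to record | Reported if related | Yes, no time limit given |

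The mismatch is the non-serious cell for days 8 to 30, a period in which the subject still has a scheduled visit. It lasts 30 − 8 + 1 = 23 days, or 23/30 = 77% of the 30 post-dose days. This is a share of calendar days.

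**2. Does other text close the gap?** Section 9.2.3 does not make T/TE events serious by definition. The important-medical-event route depends on medical judgment. No readable text extends the AE period for T/TE events. Section 5.5.2 refers to Appendix 2 for diagnosis and management, but only its heading can be read.

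**3. Does the SAP help?** It lists all recorded AEs by subject and summarizes injection site reactions separately, but Appendix I plans no T/TE table or listing. A late event would also be classified inconsistently. Protocol Section 7.4 extends treatment emergence to 7 days after the last dose. The text of SAP Section 5.8.1 drops that extension, and the algorithm in SAP Appendix III has no upper limit. Since only treatment-emergent events are summarized, a dedicated listing is the safer place for a late T/TE event.

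**4. Last visit against the SAE window.** The visit is due "1 month (30 ± 2 days) after the last dose of study drug".

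- Earliest date: 30 − 2 = day 28. Latest date: 30 + 2 = day 32.
- Largest shortfall against the day-30 SAE limit: 30 − 28 = 2 days. It arises only for visits on day 28 or 29.

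**5. Supplemental doses.** Section 6.12.1 allows a supplemental dose through 1 week post-treatment. If one is given 7 days after dose 24, and the SAE window runs from it, the window ends on day 7 + 30 = 37 after dose 24. If the visit is timed from dose 24 (an assumption, because the text does not say), it falls between 37 − 32 = 5 and 37 − 28 = 9 days before the window ends.

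**6. Pharmacological context.** Section 1.1.2 gives a half-life of about 60 hours for functional activity. Day 7 is 168/60 = 2.8 half-lives, so 0.5^2.8 ≈ 14% of the increment remains. For antigen (45 to 47 hours) the figure is about 8%.

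**The case against.** The strongest reply is that little would be lost in practice, and much of it stands.

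- **A reader might infer that such an event cannot trigger the halt.** The text does not support that. Section 5.5.2 depends on the event occurring, not on an AE page. An investigator who learns of a T/TE event on day 20 is still bound by it, and under Section 10 the sponsor's Medical Monitor reviews safety information as it arrives.
- **A reader might infer that the event would go uncaptured.** This also goes too far. AE questioning continues to the 1-Month visit, and drug treatment for a thrombosis would appear with its indication among the concomitant medications. The CRF itself is not in the documents. What holds is that recording as an AE is not required.
- **A reader might take 77% as a share of risk.** It counts days. The drug increment has largely cleared by day 7, so a short window for non-serious AEs in general is defensible.
- **A reader might see a similar gap at the 1-Week visit, which may fall on day 6.** There is none. A day-7 AE is within the collection period, and the 1-Month visit asks about events since the previous visit.
- **The early 1-Month visit does not remove the SAE duty.** Reporting runs from first awareness, so only active questioning is lost, for at most 2 days. This is separate from the T/TE mismatch.

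The affected set is also narrow. The event must be thrombotic, start on days 8 to 30 and be judged non-serious. For the halt to matter, enrollment must still be open, and it closes once six subjects have completed 12 weeks. Early completers and subjects who discontinue early can be in follow-up before then.

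None of this reconciles Section 5.5.2 with Schedule 3, footnote e.

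**Conclusion.** The point holds as a minor mismatch between two rules. For days 8 to 30 the protocol states no duty to record a T/TE event judged non-serious, although the same event falls within its enrollment halt. The expected number of such events cannot be derived from the documents. It is probably small, because many T/TE events will be judged serious; Section 1.1.2 gives only serious thrombotic events for the overseas open-label study.

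The conclusion assumes that Appendix 2 contains no recording or reporting instruction covering these days, and that sites apply footnote e as written. If Appendix 2 does contain one, only a cross-reference is missing.

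The visit-window point is secondary: at most 2 days without active questioning, with the SAE duty intact. It grows to 5 to 9 days only if a supplemental dose is given 7 days after dose 24, the SAE window runs from that dose, and the visit is timed from dose 24.

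**What to change.** 1. In the Synopsis, Sections 3 and 6.2 and Schedule 3, footnote e, add that all T/TE events, serious or not, are recorded and reported to the sponsor through 30 days after the last dose, and that subjects are asked about them at the 1-Month visit. Check the wording against Appendix 2.
2. Add one listing of all T/TE events to SAP Appendix I, whatever their treatment-emergent status.
3. Secondary: set the 1-Month window so that the visit falls on or after day 30. State whether the last dose includes supplemental doses, and use the same reference dose for the visit and the SAE window.

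The cost is protocol and SAP wording, an occasional extra AE page, one listing, and a last visit that may fall a few days later. No visit, sample or procedure is added, and the dosing and stopping rules are unchanged.

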1 INTRODUCTION

Hereditary angioedema (HAE) is a rare, autosomal dominant disease caused by an inherited or spontaneous gene mutation on chromosome 11 that results in a quantitative or functional deficiency of C1 inhibitor (C1 INH) protein (Bernstein 2011). C1 inhibitor is a serine protease inhibitor (or "serpin") that regulates the activity of several components of the complement, contact (bradykinin-forming), and fibrinolytic systems (Kaplan 2010). Dysregulation of these cascades (particularly the contact system) due to C1 INH deficiency causes the uninhibited production of bradykinin, which promotes inflammation through increased vascular permeability and excessive accumulation of fluid in body tissues (Kaplan and Joseph 2010). Thus, patients with HAE are susceptible to recurrent episodes of debilitating swelling throughout the body. Replacement of C1 INH through intravenous (IV) administration of CINRYZE® (C1 inhibitor [human]) increases serum concentrations of C1 INH antigen (protein volume) and functional C1 INH activity (potency), temporarily restoring the natural regulation of the complement, contact (bradykinin-forming), and fibrinolytic systems. C1 inhibitor replacement therapy can prevent the occurrence of angioedema attacks associated with HAE or stop and control the mechanism that causes swelling if an attack does occur.

Most HAE patients have a positive family history of angioedema, but the disease also occurs spontaneously, with de novo mutations accounting for approximately 25% of cases (Bowen et al. 2010). Symptoms typically first appear during childhood or adolescence, worsen during puberty, and persist throughout a patient's lifetime (Lumry 2013). Angioedema attacks can affect the face, tongue, larynx, gastrointestinal tract, genitourinary system, and extremities (Zuraw 2008). Gastrointestinal involvement can mimic an acute surgical emergency, and misdiagnosis often results in unnecessary procedures to remove normal appendices and gallbladders (Weis 2009). Laryngeal swelling can occlude the airway and cause death by asphyxiation.

The frequency and severity of angioedema attacks vary widely, even among members of the same family, and are unrelated to the degree of C1 INH deficiency or dysfunction. Although it is often unclear what precipitates attacks, commonly cited triggers include trauma, physical and psychological stress, medical, surgical, or dental procedures, menstruation, infections, use of estrogen-containing oral contraceptives, and angiotensin-converting enzyme (ACE) inhibitors (Longhurst and Nzeako 2012).

The estimated prevalence of HAE is 1:50,000 people worldwide (range: 1:10,000 to 1:150,000) (Horiuchi et al. 2012; Bowen et al. 2008). However, the current medical literature reflects far fewer identified cases in Japan. In 2009, a nationwide prevalence survey of 1389 larger hospitals in Japan identified 52 patients with HAE (Iwamoto et al. 2011). Yamamoto et al. (2012) reviewed the medical literature from 1969 to 2010 and identified 132 unique Japanese patients

The World Health Organization disease classification for C1 INH deficiency is D84.1, "Defects in the Complement System," under "Other Immunodeficiencies" in "Diseases of the Blood and Blood-forming Organs and Certain Disorders Involving the Immune Mechanism" (ICD-10, Version 2010). The Japan Nanbyo Research Foundation classifies C1 INH deficiency as a subcategory of Specified Rare and Intractable Disease (Tokutei Shikkan) No. 35, Primary Immunodeficiency Syndrome.

Protocol 0624-209 with Amendments 1, 2, 3, 4, CINRYZE (C1 inhibitor [human])

with HAE. Although the prevalence of patients with HAE appears to be lower in Japan, the distribution and pattern of C1 INH mutations and clinical features of the patients identified appear to be similar to Western populations (Yamamoto et al. 2012).

The burden of HAE on patients and family members is considerable with respect to its detrimental effects on physical health, career and work productivity (missed days), education (missed days), and mental health (feelings of panic and anxiety) (Aygören-Pürsün et al. 2012; Caballero et al. 2014; Lumry et al. 2010). Individual patients may be debilitated by their symptoms for up to 100 days per year, making employment or education difficult (Nzeako et al. 2001). Because of its unpredictability, HAE can be life-altering regardless of angioedema attack frequency. Patients live in constant fear of the next attack, and often arrange their lives around these events. Some patients who have had laryngeal attacks, or who have had family members die due to laryngeal attacks, never leave their local environment for fear of being distant from the safety of their home and the physicians who know and understand their illness (Levi et al. 2006).

The only product approved in Japan for the management of patients with HAE is Berinert P, a human C1 inactivator indicated to treat acute attacks of HAE. There is no approved therapy in Japan for long-term C1 INH protein replacement or prevention of angioedema attacks in patients with HAE. Given the questionable safety and efficacy of unapproved therapies currently being used to prevent angioedema attacks in Japan (ie. danazol, tranexamic acid), an unmet medical need exists for a subset of Japanese patients who experience frequent or life-threatening attacks and are not adequately managed with repeated acute treatments. CINRYZE is the only C1 INH protein replacement therapy in the world that is approved for both long-term (routine) prevention of angioedema attacks and treatment of acute attacks in patients with HAE. Routine replacement of C1 INH in patients who experience frequent attacks, severe attacks, and/or larvngeal attacks has been associated with improved patient outcomes, including a reduction in potential mortality, number of hospitalizations, and increased quality of life (eg, relief from anxiety, flexibility to travel, freedom to pursue educational and professional goals) (Craig et al. 2009; Kalfus et al. 2012; Gower et al. 2012). Consequently, international consensus guidelines have endorsed longterm replacement of C1 INH in the appropriate patient populations (Cicardi et al. 2012; Bowen 2011; Bowen et al. 2010).

